**Special handling for vitals signs and spirometry:**

- Day 1 post-dose measurements by hour, assign analysis visit = nominal visit.

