### 9.1.1.2 Treatment Cohort

Subjects at sites activated by the time of their applicable Study 115B visit (Section 9.1.1.1) may return within 1 calendar day to complete the remaining Day 1 assessments specific to Study 116 (including administration of the Day 1 dose). Predose vital sign and spirometry assessments must be repeated before dosing on the following calendar day.

Subjects who were enrolled but had Day 1 LUM/IVA administration procedures (Section 9.6) delayed more than 1 calendar day will repeat all assessments that were specified to be performed at the Day 1 visit before receiving their first dose of LUM/IVA (except for the OE if it was performed within the last 3 months before the visit).

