#### Treatment Cohort

**Continuous variables** will be summarized using descriptive summary statistics: number of subjects, mean, standard deviation (SD), standard error (SE), median, minimum value (Min), and maximum value (Max). Precisions of the summary for continuous variables are detailed in [Appendix B](#).

**Categorical variables** will be summarized using counts and percentages. Percentages will be presented to 1 decimal place.

**Baseline:** The baseline value is defined as the most recent non-missing measurement (scheduled or unscheduled) before intake of the first dose of study drug in Study 115B, except specified otherwise.

- For ECGs, the baseline will be defined as the average of the pretreatment measurements on the start of Study 115B.
- For LCI-related parameters, the values at each visit will be calculated from the technically acceptable replicates. The baseline of LCI will be the most recent non-

missing value calculated from the technically acceptable replicates before the initial administration of study drug in the Study 115B.

- For sweat chloride, the values at each visit will be based on the averaged measurements from left and right arms. The baseline is defined as the average of the values at screening and the pretreatment measurement on Day 1 of Study 115B. For assessments where there is only 1 pre-first dose sweat chloride measurement available, that measurement will be considered the baseline.

**Change (Absolute Change) from baseline** will be calculated as

$$\text{Post-baseline value} - \text{Baseline value.}$$

**Relative change from baseline** will be calculated and presented in percentage as

$$100 \times (\text{Post-baseline value} - \text{Baseline value}) / \text{Baseline value.}$$

**Unscheduled visits:** Unscheduled visit measurements will be included in the analysis as follows:

- In scheduled visit windows per specified visit windowing rules.
- In the derivation of baseline measurements.
- In individual subject data listings as appropriate.

**Visit windowing rules:** [Appendix C](#) defines the visit window mapping rules to derive the analysis visits for study 116.

Repeated observations within the same visits window:

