#### 10.5.4 Vital Signs

For the vital signs measurements, the raw values and change from parent study baseline values will be summarized at each scheduled time point of the Current Study Period (including all measurements from Study 116) based on the 116 Safety Set: systolic and diastolic blood pressure (mm Hg), body temperature (°C), pulse rate (beats per minute), respiratory rate (breaths per minute), as well as weight, stature, and BMI.

The number and percentage of subjects meeting the defined threshold criteria during the Treatment-emergent Period of the Current Study Period will be summarized based on 116 Safety Set. The threshold criteria are provided in [Appendix F](#).

Potentially abnormal SBP and DBP by their percentiles adjusted for sex, age and stature will be provided, including

- Number and percentage of subjects with categories:  $\geq 90\%$ - $<95\%$ ,  $\geq 95\%$ - $<99\%$  + 5 mmHg and  $\geq 99\%$  + 5 mmHg during the treatment-emergent period of the Current Study Period
- Number and percentage of subjects with SBP and DBP percentiles  $\geq 95\%$  once and twice during the treatment-emergent period of the Current Study Period
- Number and percentage of subjects with SBP and DBP percentiles  $\geq 95\%$  at each visit in the Current Study Period

The stature adjustment will be based on stature-for-age z-scores and their corresponding percentiles using the standard normal distribution ([Appendix H](#)). The stature percentiles will be further mapped per the following rules:

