### **10.5.7 Spirometry**

Spirometry data will be summarized descriptively at each Study 116 visit based on the 116 Safety Set for subjects who are  $\geq 3$  years of age at screening in Study 115B based on 116 FAS. Spirometry measurements from subjects who turn 3 years of age during the Study 115B or Study 116 will not be included in the summary. The raw values and absolute change/relative change from parent study baseline will be summarized at each scheduled time point of the Current Study Period.

The following parameters: forced expiratory volume in 1 second (FEV1 (L)), percent predicted FEV1 (ppFEV1), forced vital capacity (FVC (L)), percent predicted FVC (ppFVC), FEV1/FVC and ppFEV1/FVC as well as forced expiratory flow (FEF25%-75% (L/s)) and percent predicted FEF (ppFEF25%-75%) will be summarized using descriptive statistics at each visit in the Current Study Period. The percent predicted values ppFEV1, ppFVC, ppFEV1/FVC and ppFEF25%-75% will be calculated using the standards of Global Lungs Initiative (GLI) as described in [Appendix G](#).

In addition, a listing containing individual subject data will be provided.

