e Telephone contacts will be made to assess the subject’s status, any AEs, medications, treatments, and procedures.  
f If subjects can stand unassisted and follow directions, stature should be measured as height; otherwise, stature will be measured as length. Stature and weight must be measured with shoes off and while wearing light clothing. BMI will be derived from this assessment. See Section 11.4.3 of the protocol for details.  
g The subject should rest for at least 5 minutes before having vital signs and pulse oximetry measured. See Section 11.6.4 of the protocol for details.  
h Vital signs will be measured predose and at 1 hour (± 15 minutes), 2 hours (± 15 minutes), and 4 hours (± 15 minutes) postdose on Day 1.  
i An OE will be conducted by a licensed ophthalmologist. Subjects with documentation of bilateral lens removal do not need the OE. See Section 11.6.6 of the protocol for details.  
j Subjects may complete the OE within ± 1 week of the scheduled visit.

- k An OE will be conducted at the Week 96 Visit (or the ETT Visit if the subject does not have a Week 96 Visit, unless the discontinuation is due to initiation of treatment with commercially-available LUM/IVA), or the Safety Follow-up Visit.
- l Symptom-directed PEs will occur at any time during the study if triggered by AEs or if deemed necessary by the investigator. See Section 11.6.4 of the protocol for details.
- m An abbreviated PE will be performed 4 hours ( $\pm$  30 minutes) postdose on Day 1. See Section 11.6.4 of the protocol for details

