s The LCI assessment (only subjects who are ≥3 years of age at Study 115B screening who consent/assent to the optional LCI Substudy in Study 115B and Study 116) should be performed pre-bronchodilator. See Sections 11.1 and 11.4.2 of the protocol for details. The assessment will be performed in multiple replicates and before the spirometry assessment.

t Spirometry (only subjects who are ≥3 years of age at Study 115B screening) should be performed pre-bronchodilator. See Sections 11.1 and 11.6.7 of the protocol for details.

u Day 1 spirometry will be performed before LUM/IVA dosing and at 2 hours (± 30 minutes) and 4 hours (± 30 minutes) postdose.

- v Other events related to outcome include assessments relating to pulmonary exacerbations, administration of antibiotic therapy for sinopulmonary signs or symptoms, and hospitalizations (Section 11.4.4 of the protocol).
- w LUM/IVA will be administered q12h ( $\pm$  2 hours) within 30 minutes of consuming fat containing food (Section 9.6 of the protocol). On days of scheduled visits, the dose will be administered at the site after predose assessments have been completed. The last dose will be the dose administered before the Week 96 Visit. See Section 9.6 of the protocol for dose determination details.

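### No paired change from the Study 116 Day 1 pre-dose value is specified for the Day 1 post-dose spirometry and vital signs; the only planned change is from the Study 115B baseline, about 26 weeks earlier

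*SAP*

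**What the plan says.** **What is collected.** The schedule of assessments (Protocol Table 3-1, repeated in SAP Table 13-1) gives the Day 1 spirometry times: "Day 1 spirometry will be performed before LUM/IVA dosing and at 2 hours (± 30 minutes) and 4 hours (± 30 minutes) postdose". For vital signs it says "Vital signs will be measured predose and at 1 hour", and then at 2 h and 4 h. Protocol 9.1.1.2 covers subjects who return within one calendar day to finish Day 1: "Predose vital sign and spirometry assessments must be repeated before dosing on the following calendar day".

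**How it is mapped.** Under its special handling for vital signs and spirometry, SAP Appendix C says "Day 1 post-dose measurements by hour, assign analysis visit = nominal visit". That line only assigns visits and names no baseline. In Table 13-3 the first window is (1, 50] for vital signs and (1, 92] for spirometry, with study days counted from the first Study 116 dose. Neither window contains Day 1, and no rule is given for the pre-dose value.

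**What change is computed.** SAP 10.1 defines the baseline as the "most recent non-missing measurement (scheduled or unscheduled) before intake of the first dose of study drug in Study 115B". It lists exceptions for ECG, LCI and sweat chloride, but none for spirometry or vital signs. SAP 10.5.7 then says of spirometry: "The raw values and absolute change/relative change from parent study baseline will be summarized at each scheduled time point of the Current Study Period". SAP 10.5.4 says of vital signs that "the raw values and change from parent study baseline values will be summarized at each scheduled time point of the Current Study Period". Protocol 12.3.4.4 and 12.3.4.7 use the same reference, there called the Cumulative Study Baseline.

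**The concern.** Day 1 of Study 116 is a restart of drug after a planned two-week washout. The protocol obtains a pre-dose value, makes sites repeat it if dosing moves to the next day, and then measures again over the following hours. Data of that shape answer one question directly: how far did this child's value move after the dose? The natural summary is post-dose minus pre-dose within subject.

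The SAP does not specify that summary. A change at 2 h or 4 h measured from the Study 115B baseline carries 24 weeks of earlier treatment and a washout along with any acute effect. For spirometry in litres and for unadjusted vital signs it also carries about half a year of growth in a young child. Spirometry and vital signs are both components of the primary safety endpoint, and SAP 10.5.1 makes respiratory symptoms and events adverse events of special interest. An acute mean shift that the data could show would be reported only in a diluted and noisier form.

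**Working it through.** The plan states no SD, correlation or effect size for these measures, so there is no figure of its own to reproduce. The check has four steps.

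**1. Interval between the two possible references.** Study 115B treatment lasts 24 weeks (Protocol 8.1) and the planned washout 2 weeks (SAP 9.2). 24 + 2 = 26 weeks, or 26 × 7 = 182 days. Any rollover gap, whose length is not stated, adds to this. From the Day 1 pre-dose value the interval would be 1 to 4 hours for vital signs and 2 to 4 hours for spirometry.

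**2. Shift in the mean, FEV1 in litres.** Let d be the net drift from the Study 115B baseline to Day 1 pre-dose, and a the acute fall as a fraction of the pre-dose value. The planned relative change is (1 + d)(1 − a) − 1. The documents give no d, so it is an assumption. If growth were 8%, 12% or 15% per year, growth alone over half a year would be 1.08^0.5 − 1 = 3.9%, 1.12^0.5 − 1 = 5.8% or 1.15^0.5 − 1 = 7.2%. Taking d from 0 to 8%:

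| Assumed drift d | Shown if true fall is 3% | 5% | 10% |
|---|---|---|---|
| 0% | −3.0% | −5.0% | −10.0% |
| +3% | −0.09% | −2.15% | −7.3% |
| +5% | +1.85% | −0.25% | −5.5% |
| +8% | +4.76% | +2.6% | −2.8% |

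For example, 1.05 × 0.95 − 1 = −0.25%. This table applies to litres. The documents support no comparable figure for vital signs, and none is offered here.

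**3. Spread.** With equal variances at each time, SD(change) = SD × sqrt(2(1 − r)). The ratio of the planned SD to the paired same-day SD is therefore sqrt((1 − r_long)/(1 − r_day)). Both correlations are assumptions: r_long (26 weeks) 0.5 to 0.8 and r_day (same day) 0.85 to 0.95.

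- Smallest ratio: sqrt(0.20/0.15) = 1.15
- Largest ratio: sqrt(0.50/0.05) = 3.16

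**4. What could be recovered from the planned tables.** Suppose a Day 1 pre-dose row is shown and the same subjects contribute to both rows. For absolute change the common baseline B cancels, since (post − B) − (pre − B) = post − pre, so the mean acute change can be had by subtraction. For relative change the denominator remains B. At d = +5% and a = 5% the rows read +5% and −0.25%, a difference of −5.25 points against a true −5%, so the mean is nearly recovered. Subtracting two means gives no SD of the paired difference, and if different children are missing at the two times it is not a paired estimate. It also depends on a pre-dose row that Appendix C does not define.

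**The case against.** There is a fair case on the other side, and much of it stands.

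- **Raw values are planned.** SAP 10.5.4 and 10.5.7 summarise raw values at each scheduled time point, and individual values are listed. Pre-dose Day 1 is a scheduled assessment, and the Current Study Period begins on the date of the first dose, so it can be read as one of those time points. A reader might infer that the acute response is lost, or that a real fall must be hidden. The documents do not support that: the data are kept, and the raw rows carry no growth offset.
- **Percent predicted values are also summarised.** SAP 10.5.7 and Appendix G include GLI percent predicted values, which are meant to account for growth, and SAP 10.5.4 gives blood pressure percentiles adjusted for sex, age and stature. The growth argument therefore does not extend to every parameter. Prior treatment and washout still enter the change in percent predicted values, and the change tables for vital signs have no adjustment.
- **The protocol sets the same baseline.** It would be wrong to read this as an SAP departure. SAP section 4 does, however, allow for analyses beyond those in the protocol.
- **Acute effect is not a stated objective.** The objective is long-term safety, safety is descriptive, and the Day 1 measurements also fit on-site monitoring at restart. Nowhere do the documents call Day 1 a pre/post comparison. Acute events are captured as adverse events, and the special-interest events are summarised with time to first onset. Those count events; they do not measure a change.
- **Yield is limited for spirometry.** About 50 subjects are expected, only those aged at least 3 years at Study 115B screening are tested, and Protocol 9.3.3 anticipates reproducible results in a minority. This limits precision, but it applies equally to the planned change score. Vital signs are not restricted in this way.

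**Conclusion.** The point holds as a gap in specification: no paired change from the Study 116 Day 1 pre-dose value is planned, and that value has no analysis visit. What the SAP tabulates instead spans about 26 weeks as planned, and longer with any rollover gap.

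The size is illustrative. In FEV1 (L), an assumed drift of +3% to +8% would turn a 5% acute fall into an apparent change of −2.15% to +2.6%. Under the assumed correlations, the planned change would have about 1.2 to 3.2 times the SD of the paired change. Drift and correlations are assumptions, and no magnitude is claimed for vital signs or percent predicted values.

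No planned inference changes, because safety is not tested. It is worth correcting because the measures belong to the primary endpoint, the paired summary is less confounded and probably more precise, and the data are already being collected.

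**What to change.** In SAP 10.5.4, 10.5.7 and Appendix C:

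1. Define the last value before the first Study 116 dose as an additional reference, used only for the Day 1 post-dose time points. State that it may be a value taken at a same-day Study 115B Safety Follow-up Visit, since Protocol 9.1.1.1 says shared assessments need not be repeated.
2. Give that value its own analysis visit in Table 13-3.
3. Add a descriptive summary of absolute change from it at 2 h and 4 h for spirometry, with relative change as well, and at 1 h, 2 h and 4 h for vital signs. Show the number of subjects with both values of each pair.
4. Keep the Study 115B baseline for all other visits.

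The cost is SAP wording and one extra table block. The spirometry part may rest on few children, and the paired count will show how few.

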## Appendix D: Imputation Rules for Missing Prior/Concomitant Medication Dates

Imputation rules for missing or partial medication start/stop dates are defined below:

1. Missing or partial medication start date:
  - a. If only DAY is missing, use the first day of the month.
  - b. If DAY and Month are both missing, use the first day of the year.
  - c. If DAY, Month and Year are all missing, use a date before the first dose date.
2. Missing or partial medication stop date:
  - a. If only DAY is missing, use the last day of the month.
  - b. If DAY and Month are both missing, use the last day of the year.
  - c. If DAY, Month and year are all missing, assign ‘continuing’ status to stop date.

In summary, the prior, concomitant or post categorization of a medication is described below.

**Table 13-4 Prior, Concomitant, and Post Categorization of a Medication**

Medication Start Date	Medication Stop Date		
	< First Dose Date of Study Drug	≥ First Dose Date and ≤ End Date of Treatment-emergent Period	> End Date of Treatment-emergent Period
< First dose date of study drug	P	PC	PCA
≥ First dose date and ≤ End date of Treatment-emergent period	-	C	CA
> End date of Treatment-emergent period	-	-	A

A: Post; C: Concomitant; P: Prior

## **Appendix E: Imputation Rules for Missing AE dates**

Imputation rules for missing or partial AE start date are defined below:

### **If only Day of AE start date is missing:**

If the AE start year and month are the same as that for the first dose date, then:

- If the full (or partial) AE end date is NOT before the first dose date or AE end date is missing, then impute the AE start day as the day of first dose date; otherwise, impute the AE start day as 1.
- Otherwise, impute the AE start day as 1.

Compare the imputed AE start date with Treatment-Emergent period to determine whether the AE is pretreatment AE, TEAE or post-treatment AE.

### **If Day and Month of AE start date are missing:**

If AE start year = first dose year, then:

- If the full (or partial) AE end date is NOT before the first dose date or AE end date is missing, then impute the AE start Month and Day as the Month and Day of first dose date; otherwise, impute the AE start Month as January and the Day as 1.
- Otherwise, impute the AE start MONTH as January and the DAY as 1.

Compare the imputed AE start date with Treatment-Emergent period to determine whether the AE is pretreatment AE, TEAE or post-treatment AE.

### **If Year of AE start date is missing:**

If the year of AE start is missing or AE start date is completely missing then query site with no imputation. Also compare the full (or partial) AE end date to the first dose date. If the AE end date is before the first dose date then the AE should be considered as a pretreatment AE. Otherwise, the AE will be considered as TEAE.

## Appendix F: Criteria for Threshold Analysis

**Table 13-5 Threshold Analysis Criteria for Laboratory Tests**

Parameter	Categorical change	Comments
Clinical Chemistry		
ALT	$\leq 3xULN$ *(Not a categorical change) $>3x - \leq 5xULN$ $>5x - \leq 8xULN$ $>3xULN$ $>5xULN$ $>8xULN$	FDA DILI Guidance Jul 2009.
AST	$\leq 3xULN$ *( Not a categorical change) $>3x - \leq 5xULN$ $>5x - \leq 8xULN$ $>3xULN$ $>5xULN$ $>8xULN$	FDA DILI Guidance Jul 2009.
ALT or AST	ALT $>3xULN$ or AST $>3xULN$	Vertex LFT working group 2014
ALT or AST	ALT $>5xULN$ or AST $>5xULN$	
ALT or AST	ALT $>8xULN$ or AST $>8xULN$	
Alkaline Phosphatase	$>1.5xULN$	FDA DILI Guidance Jul 2009.
Total Bilirubin	$>1.5x - \leq 2xULN$ $>2xULN$	FDA DILI Guidance Jul 2009.
ALT and Total Bilirubin	ALT $>3xULN$ and TBILI $>2xULN$	FDA DILI Guidance Jul 2009. To be counted within a same treatment phase, whatever the interval between measurements.
AST and Total Bilirubin	AST $>3xULN$ and TBILI $>2xULN$	FDA DILI Guidance Jul 2009. To be counted within a same treatment phase, whatever the interval between measurements.
(ALT or AST) and Total Bilirubin	(ALT $>3xULN$ or AST $>3xULN$ ) and TBILI $>2xULN$	Vertex LFT working group 2014
CPK	$>3x - \leq 10xULN$ $>10xULN$	FDA criteria Feb 2005. Am J Cardiol April 2006.
Creatinine	$\geq 150 \mu\text{mol/L}$ (Adults) $\geq 30\%$ change from baseline $\geq 100\%$ change from baseline	Benichou C., 1994.
Blood Urea Nitrogen	$\geq 17 \text{ mmol/L}$	
Chloride	$<85 \text{ mmol/L}$ $>115 \text{ mmol/L}$	
Sodium	$\leq 129 \text{ mmol/L}$ $\geq 150 \text{ mmol/L}$	

Potassium	<3 mmol/L ≥5.5 mmol/L	FDA Feb 2005.
Glucose		
Hypoglycaemia	≤3.9 mmol/L and <LLN	ADA May 2005.
Hyperglycaemia	≥11.1 mmol/L (unfasted); ≥7 mmol/L (fasted)	ADA Jan 2008.
Albumin	≤25 g/L	
Hematology		
WBC	<3.0 Giga/L (Non-Black); <2.0 Giga/L (Black) ≥16.0 Giga/L	Increase in WBC: not relevant. To be interpreted only if no differential count available.
Lymphocytes	>4.0 Giga/L	
Neutrophils	<1.5 Giga/L (Non-Black); <1.0 Giga/L (Black)	International Consensus meeting on drug-induced blood cytopenias, 1991. FDA criteria.
Monocytes	>0.7 Giga/L	
Basophils	>0.1 Giga/L	
Eosinophils	>0.5 Giga/L or >ULN (if ULN ≥0.5 Giga/L)	Harrison- Principles of internal Medicine 17th Ed., 2008.
Hemoglobin	≤115 g/L (Male); ≤95 g/L (Female) ≥185 g/L (Male); ≥165 g/L (Female)  Decrease from Baseline ≥20 g/L	Criteria based upon decrease from baseline are more relevant than based on absolute value. Other categories for decrease from baseline can be used (≥30 g/L, ≥40 g/L, ≥50 g/L).
Hematocrit	≤0.37 v/v (Male) ; ≤0.32 v/v (Female) ≥0.55 v/v (Male) ; ≥0.5 v/v (Female)	
RBC	≥6 Tera/L	
Platelets	<100 Giga/L ≥700 Giga/L	International Consensus meeting on drug-induced blood cytopenias, 1991.

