## 5.2 Study Rationale

Approximately half of the total CF patient population is <18 years of age. Even before the widespread adoption of newborn screening, the majority of patients with CF were diagnosed in infancy or early childhood due to manifestations of the disease. Pancreatic destruction leading to pancreatic exocrine insufficiency begins in utero, and lung involvement is manifest by pulmonary inflammation and infection that begins shortly after birth.

The primary objectives of Study VX15-809-115 (Study 115) are to obtain pharmacokinetic (PK) and safety information to support a proposed indication expansion of LUM/IVA in subjects aged 2 through 5 years, homozygous for *F508del*. The primary objective of Study VX16-809-116 (Study 116) is to evaluate the long-term safety of LUM/IVA in subjects aged 2 years and older with CF, homozygous for *F508del*, who participated in Study 115.

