### 9.3 Rationale for Study Design and Study Drug Regimens

### 9.3.1 Study Design

Vertex has established efficacy, safety, and PK profiles for LUM/IVA in subjects 12 years of age and older, homozygous for *F508del* (Studies VX12-809-103 [Study 103] and VX12-809-104 [Study 104]). Because the underlying genetic and molecular etiology of the disease is identical between younger and older patients, and the outcome of therapy is likely to be comparable, extrapolation of efficacy from older to younger patients is appropriate and PK studies in younger patients, together with safety studies, can provide adequate information for use. 9

Safety and PK profiles for LUM/IVA have been established in subjects 6 through 11 years of age, homozygous for *F508del* (Study VX13-809-011 [Study 011]). Study 115, a Phase 3, 2-part, open-label study, which includes a 24-week Treatment Period in Part B, is designed to obtain PK and safety information to support a proposed indication expansion of LUM/IVA in subjects aged 2 through 5 years, homozygous for *F508del*.

Study 116 is a Phase 3, open-label, multicenter study in subjects aged 2 years and older with CF, homozygous for *F508del*, who participated in Study 115B. This study, which includes a 96-week Treatment Period, is designed to evaluate the long-term safety of LUM/IVA in subjects aged 2 years and older with CF, homozygous for *F508del*.

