### **Analysis Period**

Cumulative Study Period starts from the first dose of study drug in the previous study to the last day in Study 116, regardless of 1) the planned 2-week Washout Period in Study 115B; or 2) the rollover gap between Study 115B and Study 116. For subjects not enrolled in Study 116, the Cumulative Study Period will start from the first dose of study drug in the previous study to the last day in the previous study.

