## 13.1.1.4 Adverse Event Severity

The investigator will determine and record the severity of all serious and nonserious AEs. The guidance available at the following website will be consulted: Common Terminology Criteria for Adverse Events (CTCAE), Version 4.0, Cancer Therapy Evaluation Program, http://ctep.cancer.gov/protocolDevelopment/electronic\_applications/ctc.htm (Accessed September 2016). AEs of CTCAE Grades 4 and 5 will be documented as "life-threatening." In considering the severity of an AE in a pediatric subject, the investigator will consider that reference ranges for pediatric clinical laboratory parameters may differ from those given in the CTCAE. The severity of an AE that does not appear in the CTCAE will be determined according to the definitions in Table 13-1.

**Table 13-1** Grading of AE Severity

Classification	Definition
Mild (Grade 1)	Mild level of discomfort and does not interfere with regular activities
Moderate (Grade 2)	Moderate level of discomfort and significantly interferes with regular activities
Severe (Grade 3)	Significant level of discomfort and prevents regular activities
Life-threatening (Grade 4)	Any adverse drug event that places the subject, in the view of the investigator, at immediate risk of death

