**Table 13-6 Threshold Analysis Criteria for ECGs**

Parameter	Categorical change	Comments
HR	$\leq 50$ bpm and decrease from baseline $\geq 20$ bpm $\geq 120$ bpm and increase from baseline $\geq 20$ bpm $< 40$ bpm $< 50$ bpm $> 90$ bpm	
PR	$\geq 220$ ms and increase from baseline $\geq 20$ ms	
QRS	$\geq 120$ ms	
QTc	Absolute values (ms)	To be applied to any kind of QT correction formula.
Borderline	Borderline: 431-450 ms (Male); 451-470 ms (Female)	
Prolonged*	Prolonged: $> 450$ ms (Male); $> 470$ ms (Female)	
Additional	$\geq 500$ ms  Increase from baseline Borderline: Increase from baseline 30-60 ms Prolonged: Increase from baseline $> 60$ ms	

Note: Based on CPMP 1997 guideline.

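### Some fixed cut-offs in SAP Appendix F do not suit children aged about 2 to 8: the sex-split hemoglobin, hematocrit and QTc limits, the adult creatinine limit, and the standalone heart rate flag above 90 bpm

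*SAP*

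**What the plan says.** SAP 10.5.2 and 10.5.3 count the subjects in the 116 Safety Set who meet the Appendix F criteria during the Treatment-emergent Period of the Current Study Period. Laboratory values and ECGs are both part of the primary endpoint (SAP 6.1).

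The rows at issue are these:

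- **Creatinine (Table 13-5).** There are three criteria: an absolute value of 150 µmol/L labelled for adults, a change of at least 30%, and a change of at least 100%. The flattened table gives "Adults) $\geq 30\%$ change from baseline", in which the adult label closes the first criterion and the second one follows.
- **Hemoglobin, low (Table 13-5).** "≤115 g/L (Male); ≤95 g/L (Female", plus a row for a fall of at least 20 g/L. The comment beside it reads "Criteria based upon decrease from baseline are more relevant than based on absolute value".
- **Hematocrit, low (Table 13-5).** At most 0.37 in males and 0.32 in females.
- **QTc, absolute (Table 13-6).** Borderline is 431-450 ms in males and 451-470 ms in females. Prolonged is above 450 ms and above 470 ms respectively. Sex-neutral rows follow: 500 ms or more, and increases of 30-60 ms and above 60 ms.
- **Heart rate (Table 13-6).** Two rows combine an absolute value with a 20 bpm change. Standalone limits are then listed, ending "< 50$ bpm $> 90$ bpm".

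**The concern.** The parent study covers "LUM/IVA in subjects aged 2 through 5 years", so no adult can appear in these tables. A limit labelled for adults has no one to apply to. Limits that differ by sex but not by age make the count depend on a child's sex even when boys and girls have identical values. A heart rate flag with no age or baseline condition may be met so often that its count says little.

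The study has one treated group and no concurrent control, and its safety analysis is descriptive. A flag that the cut-off itself produces cannot cancel against a comparator, and a pooled percentage moves with the mix of boys and girls. Elsewhere the SAP does adjust for age: section 10.5.4 judges blood pressure by percentiles for sex, age and stature.

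**Working it through.** **Plan's own figure.** Expected enrolment: 56 × (1 − 0.10) = 50.4, which agrees with the stated 50. The plan has no power calculation to reproduce.

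**Age range.** Children are under 6.0 years at parent-study entry. The parent study is one "which includes a 24-week Treatment Period in Part B"; then come "the planned 2-week Washout Period in Study 115B" and up to 98 weeks in Study 116.

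- 24 + 2 + 98 = 124 weeks; 124 × 7 / 365.25 = 2.38 years; 6.0 + 2.38 = about 8.4 years at most.
- The length of any rollover gap is not given. With an assumed 12 weeks: 6.0 + 136 × 7 / 365.25 = about 8.6 years.

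**Same value, different flag (documents alone).**

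| Value | Boy | Girl |
|---|---|---|
| Hemoglobin above 95, up to 115 g/L | low | not flagged |
| Hematocrit above 0.32, up to 0.37 | low | not flagged |
| QTc 431-450 ms | borderline | not flagged |
| QTc 451-470 ms | prolonged | borderline |

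Hematocrit is not among the analytes in Protocol Table 11-1 as extracted, so that row matters only if the laboratory reports it.

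**Size under assumed distributions.** The documents give no pediatric distributions. Each line assumes one normal distribution shared by both sexes and gives the share of single readings flagged, Φ((cut-off − mean)/SD) or its complement.

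- Hemoglobin, mean 115-130, SD 7-10 g/L: boys 2% to 50%, girls 0% to 2.3%. Example at mean 120, SD 10: Φ(−0.5) = 30.9% and Φ(−2.5) = 0.6%.
- Hematocrit, mean 0.35-0.39, SD 0.025: boys 21% to 79%, girls 0.3% to 11.5%.
- QTc borderline or worse, mean 400-420, SD 15-20 ms: boys 2% to 31%, girls 0% to 7%.

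**Effect of the sex mix on a pooled count.** Take the hemoglobin example, 50 children and one reading each. With 20 boys: 20 × 0.309 + 30 × 0.006 = 6.4 flagged. With 30 boys: 30 × 0.309 + 20 × 0.006 = 9.4. The blood values are the same; only the mix differs.

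**Creatinine.** Read literally, the adult row counts no one. If it were applied anyway, 150/75 = 2.0, so any child with a baseline below 75 µmol/L would have to more than double to reach it and would already meet the 100% row. For assumed baselines of 20 and 50 µmol/L the rise needed is 7.5-fold and 3-fold. Below a baseline of 75 µmol/L the row adds nothing.

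**Heart rate above 90 bpm.** The share of single readings flagged is 35% at an assumed mean of 85 (SD 13), 63% at mean 95 (SD 15) and 95% at mean 110 (SD 12). Over three ECGs at mean 95, SD 15, at least one flag occurs in 1 − 0.369³ = 95% of children if readings are independent. That falls to about 85% and 80% at within-child correlations of 0.5 and 0.7.

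**The case against.** Much of Appendix F is not open to this criticism. ALT, AST, alkaline phosphatase, bilirubin and CPK are multiples of ULN, and the hypoglycemia row also requires a value below LLN. Creatinine, hemoglobin and QTc have change-from-baseline rows, and the 500 ms QTc row is the same for both sexes. A reader might infer that both tables are uninformative, or that every fixed cut-off is an adult value. The documents do not support that: only the creatinine limit carries an adult label, and no pediatric ranges are given against which to judge the rest. A reader might also take the 30% creatinine rule to be an adult rule because of how the cell was flattened; it is not.

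Other summaries help. SAP 10.5.2 already gives counts below LLN and above ULN, but by visit rather than over the treatment-emergent period. SAP 10.5.3 adds raw ECG values, changes and shifts in overall evaluation. It would therefore be wrong to say that the heart rate flag hides any signal: by-visit means and the row that combines 120 bpm with a 20 bpm rise remain.

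Protocol 13.1.1.4 cautions that "reference ranges for pediatric clinical laboratory parameters may differ from those given in the CTCAE", but it does so for investigators grading adverse events. It is context and does not govern the SAP's tables.

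Table 13-6 cites a 1997 CPMP guideline, so replacing its sex-specific QTc bands with one limit is debatable, and the documents offer no pediatric alternative.

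Finally, no test uses these counts. The Protocol's LFT and QTcF action rules (11.6.3 and 11.6.5) are based on ULN or are sex-neutral and do not refer to Appendix F.

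All of this narrows the point. It does not remove the sex-dependent hemoglobin, hematocrit and QTc counts, the row that applies to no subject, or the unconditioned heart rate flag.

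**Conclusion.** The point holds for a limited set of rows. The documents alone show that identical hemoglobin, hematocrit or QTc values are classified differently by sex in children of about 2 to 8.4 years, and that the 150 µmol/L creatinine limit applies to no one. How many children are affected is not known from the documents; the percentages above rest on assumed distributions. Over the hemoglobin range used, boys are always flagged more often than girls. How common a heart rate above 90 bpm is at these ages is also an assumption (about 35% to 95% of readings for means of 85 to 110 bpm), and it cannot be stated as fact that most healthy children meet it.

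The effect is confined to descriptive summaries of the primary safety endpoint. Severity is minor: a cheap improvement in how the tables read.

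**What to change.** In SAP Appendix F:

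1. **Hemoglobin and hematocrit.** Replace the sex-split absolute cut-offs with a treatment-emergent count of subjects outside the central laboratory's LLN/ULN for age. SAP 10.5.2 already uses LLN and ULN by visit but does not say that they are age-specific, so confirm this with the laboratory. Keep the row for a hemoglobin fall of at least 20 g/L.
2. **Creatinine.** Drop the 150 µmol/L row or mark it not applicable. Keep the 30% and 100% rows.
3. **Heart rate.** Delete the standalone row above 90 bpm. Keep the rows that also require a 20 bpm change.
4. **QTc.** Base interpretation on the sex-neutral rows (500 ms or more; increases of 30-60 ms and above 60 ms). Show the sex-split absolute bands separately for boys and girls, not only pooled.
5. **Leave unchanged** the multiple-of-ULN rows, the row that also requires a value below LLN, and the other change-from-baseline rows.

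The cost is an appendix edit and reprogramming of a few flags, with no new data. The downside is less direct comparability with the sponsor's standard threshold tables.
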